7.2.4. Clinical Safety Laboratory Assessments

The required laboratory tests are listed in [Appendix 3](#). Hematology and blood chemistry will be collected at the time points described in the [Schedule of Activities](#) table and analyzed at local laboratories. Laboratory tests may also be performed when clinically indicated. Local laboratory certification(s) and reference ranges should be provided to the Sponsor prior to study participant screening activity.

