3.5.2. Vital Signs

Vital signs data include weight, pulse rate, systolic blood pressure, and diastolic blood pressure. Measurements were only to be provided once per timepoint. If multiple assessments are provided per timepoint, the maximum value will be used for reporting. Additional details are provided in [Section 6.6.2](#).

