6.6.1. Laboratory Data

Laboratory results will be converted to International System of Units (Système International d'unités, SI) units which will be used for applying toxicity grades and for all summaries.

Quantitative data will be summarized using simple descriptive statistics (mean, Std Dev, median, quartiles, minimum, and maximum) of actual values and change from baseline for each nominal visit over time (ie, unscheduled assessments will be excluded). The total number of participants for change from baseline will include all participants who have both a baseline and a value at the nominal visit.

As described in [Section 3.4](#), baseline will be defined as the last assessment performed on or prior to date of the first dose of study treatment. If there are multiple assessments that meet the baseline definition on the same day without the ability to determine which was truly last, then the worst grade will be assigned as the baseline grade. Several of the CTCAE terms (including Hypo/Hypercalcemia, Chronic Kidney Disease, and Activated Partial Thromboplastin) can be derived using several laboratory tests (analytes).

Results collected as strict inequalities (eg, >10 , <10) will be converted to numeric values subtracting a factor of $<0.001>$. Expressions of the form " \geq " or " \leq " will be converted to the end point. These numeric values will be evaluated for clinically significant abnormalities, but will not be included in calculations of summary statistics.

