Abnormalities will be described using the worst grade by scheduled timepoint and overall. Worst case overall will be determined from scheduled and unscheduled visits. Several laboratory tests have bi-directional grading criteria defined so that both low (hypo) and high (hyper) values can be graded separately. Each criterion will be summarized separately. In the cases where a value is graded as a Grade 1, 2, 3, or 4 for one of the directions, that value will also be assigned as a Grade 0 for the opposite direction for that test. For example, a value meeting the criteria for Grade 3 Hypercalcemia will be classified as a Grade 0 Hypocalcemia. For CTCAE terms that can be derived using one of several laboratory tests, the maximum post-baseline grade for a given participant and CTCAE term will be the maximum across all possible laboratory tests.

Additional laboratory results that are not part of NCI-CTCAE will be presented according to the following categories by scheduled timepoint as well as overall: below normal limit, within normal limits, and above normal limits. In the unlikely event that for a given participant, clinically significant abnormalities are noted in both directions (eg, $>$ ULN and $<$ Lower Limit of Normal (LLN)), then both abnormalities are counted.

Liver function tests: Alanine aminotransferase (ALT), aspartate aminotransferase (AST), alkaline phosphatase (ALP), and total bilirubin (TBILI) are used to assess possible drug induced liver toxicity. The ratios of test result over the ULN will be calculated and classified for these three parameters during the on-treatment period.

Summary of liver function tests will include the following categories. The number and percentage of participants with each of the following during the on-treatment period will be summarized:

- $ALT \geq 3 \times ULN$, $ALT \geq 5 \times ULN$, $ALT \geq 10 \times ULN$, $ALT \geq 20 \times ULN$;
- $AST \geq 3 \times ULN$, $AST \geq 5 \times ULN$, $AST \geq 10 \times ULN$, $AST \geq 20 \times ULN$;
- $(ALT \text{ or } AST) \geq 3 \times ULN$, $(ALT \text{ or } AST) \geq 5 \times ULN$, $(ALT \text{ or } AST) \geq 10 \times ULN$, $(ALT \text{ or } AST) \geq 20 \times ULN$;
- $TBILI \geq 2 \times ULN$;
- Concurrent $ALT \geq 3 \times ULN$ and $TBILI \geq 2 \times ULN$;
- Concurrent $AST \geq 3 \times ULN$ and $TBILI \geq 2 \times ULN$;
- Concurrent $(ALT \text{ or } AST) \geq 3 \times ULN$ and $TBILI \geq 2 \times ULN$;

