- Concurrent $(ALT \text{ or } AST) \geq 3 \times ULN$ and $TBILI \geq 2 \times ULN$ and $ALP > 2 \times ULN$;
- Concurrent $(ALT \text{ or } AST) \geq 3 \times ULN$ and $TBILI \geq 2 \times ULN$ and $ALP \leq 2 \times ULN$ or missing.

Concurrent measurements are those occurring on the same date.

Categories will be cumulative, ie, a participant with an elevation of AST $\geq 10 \times \text{ULN}$ will also appear in the categories $\geq 5 \times \text{ULN}$ and $\geq 3 \times \text{ULN}$. Liver function elevation and possible Hy's Law cases will be summarized using frequency counts and percentages.

An evaluation of Drug-Induced Serious Hepatotoxicity (eDISH) plot will also be created, with different symbols, by graphically displaying

- Peak serum ALT(/ULN) vs peak total bilirubin (/ULN) including reference lines at ALT= $3 \times \text{ULN}$ and total bilirubin= $2 \times \text{ULN}$.
- Peak serum AST(/ULN) vs peak total bilirubin (/ULN) including reference lines at AST= $3 \times \text{ULN}$ and total bilirubin= $2 \times \text{ULN}$.

In addition, a listing of all TBILI, ALT, AST and ALP values for participants with a post-baseline TBILI $\geq 2 \times \text{ULN}$, ALT $\geq 3 \times \text{ULN}$ or AST $\geq 3 \times \text{ULN}$ will be provided.

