6.6.2. Vital Signs

Vital sign summaries will include all vital sign assessments from the on-treatment period. All vital sign assessments will be listed, and those collected outside the on-treatment period will be flagged in the listing.

All vital sign parameters will be summarized using descriptive statistics (mean, Std Dev, median, Q1, Q3, minimum, and maximum) of actual values and change from baseline for each nominal visit over time (unscheduled assessments will be excluded). The changes computed will be the differences from baseline. The total number of participants for change from baseline will include all participants who have both a baseline value and a value at the nominal visit. Baseline will be selected as defined in [Section 3.4](#).

The number and percent of participants in each of the following minimum and maximum blood pressure, body weight, and pulse categories will be presented:

- Maximum increase from baseline in Systolic Blood Pressure $\geq 40 \text{ mmHg}$;
- Maximum decrease from baseline in Systolic Blood Pressure $\leq -60 \text{ mmHg}$;
- Maximum increase from baseline in Diastolic Blood Pressure $\geq 20 \text{ mmHg}$;
- Maximum decrease from baseline in Diastolic Blood Pressure $> -40 \text{ and } \leq -20 \text{ mmHg}$;
- Maximum decrease from baseline in Diastolic Blood Pressure $\leq -40 \text{ mmHg}$;
- Maximum increase from baseline in Body Weight $\geq 10\%$;
- Maximum decrease from baseline in Body Weight $\leq -10\%$;
- Maximum post-baseline Pulse Rate $> 130 \text{ bpm}$;

- Minimum pose-baseline Pulse Rate <50 bpm;
- Maximum increase from baseline in pulse rate ≥ 30 bpm;
- Maximum decrease from baseline in pulse rate ≤ -30 bpm.

All assessments, including unscheduled assessments will be considered. A participant can be included in multiple categories if different criteria are met at different timepoints.

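### SAP 6.6.1 subtracts 0.001 from '>' laboratory results as well as '<' results, so a '>' result reported at a cut-off is classified on the wrong side of it

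*SAP*

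**What the plan says.** SAP 6.6.1 (Laboratory Data) sets the rule for results that arrive with an inequality sign: "Results collected as strict inequalities (eg, >10 , <10) will be converted to numeric values subtracting a factor of" 0.001. Both directions appear as examples, and no addition is given for '>'. Results with '≥' or '≤' are treated differently: they "will be converted to the end point".

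The same paragraph limits how the converted numbers are used: "These numeric values will be evaluated for clinically significant abnormalities, but will not be included in calculations of summary statistics".

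The classifications follow in the same section: programmatic CTCAE grading, a below/within/above normal range class for ungraded tests, and the liver function table. For the liver tests, "The ratios of test result over the ULN will be calculated and classified", and "Liver function elevation and possible Hy's Law cases will be summarized using frequency counts and percentages". Under Protocol 7.2.4 the samples are "analyzed at local laboratories", so reference ranges and reporting limits may differ between sites.

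**The concern.** A result of '>x' says that the true value is above x. Subtracting from x gives a number that the result excludes. The SAP rule therefore gives '>10' and '<10' the same value and ranks '>10' below '≥10'.

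The converted numbers never enter a mean or median, so the wrong sign cannot be passed off as a harmless 0.001 in a summary statistic. The only place it can act is a comparison with a threshold. At the ALT, AST and bilirubin thresholds of the liver table, all of the 'at or above' kind, subtraction can only hide an elevation. At stake is a count in a safety table, in a study whose primary objective is safety.

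**Working it through.** The plan gives no figure to reproduce here. The check applies the SAP's rule to its own examples and cut-offs. I read the evaluation of abnormalities in 6.6.1 as covering CTCAE grade, normal-range class and the liver rows.

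**Inputs from the SAP (6.6.1).** Constant 0.001, subtracted for both strict signs; '≥' and '≤' set to the end point. Liver cut-offs: ALT and AST at or above 3, 5, 10 and 20 × ULN; total bilirubin (TBILI) at or above 2 × ULN; ALP above 2 × ULN, or at or below 2 × ULN or missing. Liver rows: 4 ALT + 4 AST + 4 (ALT or AST) + 1 TBILI + 3 concurrent + 2 concurrent with ALP = 18.

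**Assumed.** The documents give no ULN and no assay reporting limit. The values below are illustrations only.

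**Step 1: the SAP's own examples.**
- '<10': 10 − 0.001 = 9.999, correctly below 10.
- '>10' under the SAP: 10 − 0.001 = 9.999, wrong. With the sign reversed: 10 + 0.001 = 10.001.
- '≥10': 10.

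**Step 2: when the wrong sign matters.** Take a criterion 'at or above C' and a result '>L'. The result establishes the criterion whenever L ≥ C. The SAP value L − 0.001 meets it only when L ≥ C + 0.001. The class is therefore wrong when C ≤ L < C + 0.001. For a strict criterion, 'above C', the upper end of that window is also included. The 0.001 is in whatever units the subtraction is made; 6.6.1 converts results to SI units but does not say which step comes first.

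With C = 120:
- L = 120 or 120.0005: wrong.
- L = 120.001, 121 or 150: right.
- L = 119: 118.999 or 119.001, not counted with either sign.

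**Step 3: results lying on a cut-off.**

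| Result | Assumed ULN | SAP value / ULN | SAP class | Value with +0.001 / ULN | Class |
|---|---|---|---|---|---|
| ALT '>120' | 40 | 119.999/40 = 2.999975 | not ≥3 × ULN | 120.001/40 = 3.000025 | ≥3 × ULN |
| ALT '≥120' | 40 | 120/40 = 3 | ≥3 × ULN | unchanged | ≥3 × ULN |
| TBILI '>40' | 20 | 39.999/20 = 1.99995 | not ≥2 × ULN | 40.001/20 = 2.00005 | ≥2 × ULN |
| ALP '>240' | 120 | 239.999/120 = 1.999992 | ≤2 × ULN | 240.001/120 = 2.000008 | >2 × ULN |

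The same reversal appears at every ALT multiple (3, 5, 10, 20) with assumed ULNs of 30, 40, 50 and 56, for TBILI with 17, 20 and 21, and for ALP with 100, 120 and 130. For an ungraded test, a result reported as above the ULN becomes ULN − 0.001 and is classed as within normal limits.

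**Step 4: the other direction.** With an assumed lower limit of 35, '<35' becomes 34.999 and is correctly below it. Only '>' needs changing.

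**The case against.** The strongest reply is that this is a drafting slip with almost no reach. It needs a '>' reporting limit on, or within a thousandth above, a cut-off. The examples were chosen to land there, and limits of 119, 121 or 150 show no effect. Nothing in the documents says that any '>' result is expected. All of this stands and sets the severity. It does not make the sign right, and no other part of the SAP corrects it.

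Three stronger readings are tempting, and the documents do not support them.

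- **That potential Hy's Law cases would be missed.** Under Protocol 8.6.2, sites identify these cases from laboratory results, repeat the tests, and report confirmed cases as SAEs. The SAP conversion plays no part in that. In the ALP example, a participant who already meets the transaminase and bilirubin criteria moves into the row for ALP at or below 2 × ULN or missing. That row matches the ALP condition in Protocol 8.6.2, so the error there over-counts rather than hides.
- **That the vital-signs rules have a similar directional fault.** SAP 3.5.2 says "If multiple assessments are provided per timepoint, the maximum value will be used for reporting", and some categories in SAP 6.6.2 look for decreases or minima. But 3.5.2 expects one measurement per timepoint, so this is a tie-break for unplanned data. For the categories, 6.6.2 states: "All assessments, including unscheduled assessments will be considered". The natural reading keeps duplicate readings in them. Preferring a mean to the maximum in by-visit tables is a matter of taste, and the documents give no duplicate rate or within-visit variability to argue from.
- **That the constant was left unfilled.** It is printed in angle brackets, which may come from reading the PDF. This is not counted as a fault.

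**Conclusion.** The conversion of '>' results in SAP 6.6.1 is wrong as written; the conversion of '<' results is right. The severity is low: a correction that is nice to have.

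The effect is confined to classification in SAP outputs, and to '>' limits on, or less than 0.001 above, a cut-off. How often that occurs cannot be worked out from the documents, because laboratories are local and no ULNs or reporting limits are given; it is probably rare. The ULNs in the examples are assumptions. The direction of the error does not depend on them.

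The primary and secondary results are unaffected. TEAE incidence comes from adverse events recorded by the investigator, with grades as reported on the CRF (SAP 6.1.1). ORR and DoR come from the investigator's tumor assessments. Laboratory means, medians and changes from baseline are also untouched, because converted values are excluded from them.

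**What to change.** In SAP 6.6.1, convert '<x' to x minus 0.001 and '>x' to x plus 0.001, and leave the end-point rule for '≥' and '≤' as it is. The same sentence could say whether the adjustment is made before or after conversion to SI units; the sign correction does not depend on it.

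The cost is a few words in the SAP and a trivial programming change. Data collection does not change, and SAP 3.5.2 and 6.6.2 need no change on this account.

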9.6.1. Analysis of Primary Endpoint

The primary endpoint is the incidence of AEs. AEs will be summarized by type, frequency, severity (as graded by the investigator according to NCI CTCAE version 4.03 and coded by the Sponsor using MedDRA), timing, seriousness and relationship to dacomitinib. The focus of AE summaries will be on treatment-emergent AEs, those with initial onset or increasing in severity after the first dose of study medication. The number and percentage of participants who experienced any AE, SAE, treatment-related AE, or treatment-related SAE will be summarized descriptively. AEs leading to death or discontinuation of study treatment, events classified as Grade ≥ 3 , treatment-related events, and SAEs will also be summarized. Detailed information collected for each AE will be listed with a description of the event, duration, whether the AE was serious, intensity, relationship to study treatment, action taken, and clinical outcome.

Study Treatment Exposure

Drug exposure will be summarized using descriptive statistics. The number and percentage of participants with dose reduction, temporary/permanent discontinuations and the corresponding reasons will also be summarized. The number and percentage of participants with dose reductions/modifications and the corresponding reasons will also be summarized.

Laboratory Tests

Laboratory test results will be graded according to NCI CTCAE version 4.03. Data will be summarized by the type of laboratory test. Summary of laboratory abnormalities will be presented by maximum CTCAE Grade. For laboratory tests without an NCI CTCAE grade definition, results will be categorized as normal (within normal ranges), abnormal, or not done. Shift tables will be provided to examine the distribution of laboratory abnormalities.

Vital Signs

Vital signs data will be summarized using descriptive statistics (mean, standard deviation, median, quartiles, minimum, and maximum) of actual values and change from baseline for each nominal visit over time (ie, unscheduled assessments will be excluded).

Electrocardiograms

All ECGs obtained during the study will be evaluated for safety. The triplicate data will be averaged, and all summary statistics and data presentations will use the triplicate averaged data.

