Additionally, laboratory results will be programmatically classified according to NCI-CTCAE version 4.03 grade. Non-numerical qualifiers will not be taken into consideration in the derivation of grade (eg, hypokalemia Grade 1 and Grade 2 are only distinguished by a non-numerical qualifier and therefore Grade 2 will not be derived). In summary statistics the number and percentage of participants corresponding to grades that only include non-quantitative criteria will be displayed as a blank or NA (not assessed) rather than 0. If there is any overlap between grade criteria (eg, CTCAE grading criteria for Creatinine Increased – a value can fall into one range based on comparison to Upper Limit of Normal (ULN) and another range based on comparison to baseline), the highest (worst) grade would be assigned to that record. Grade 5 is defined in the CTCAE criteria guidance as an event with an outcome of death. Since laboratory data does not collect an outcome, Grade 5 is not used when programmatically grading laboratory data.

Grade 0 or Outside Toxicity Reference (OTR) is not defined specifically by in the CTCAE guidance. However, programmatically this is used as a category to represent those participants who did not meet any of the Grades 1 to 4 criteria. If the laboratory value is evaluable for CTCAE criteria grading (numeric value is present, valid units and ranges are present as required to allow conversion to standard units and grading), and does not qualify for any of the Grade 1-4 criteria for a given lab test, then the value is assigned as Grade 0 or OTR.

Several of the CTCAE terms (including Hypo/Hypercalcemia, Chronic Kidney Disease, and Activated Partial Thromboplastin) can be derived using several laboratory tests (analytes).

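### SAP 6.6.1 drops laboratory results reported as inequalities from the by-visit descriptive tables, and those tables shift because the dropping depends on the value

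*SAP*

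**What the plan says.** SAP 6.6.1 (Laboratory Data) plans, for each nominal visit, "simple descriptive statistics (mean, Std Dev, median, quartiles, minimum, and maximum) of actual values and change from baseline". It states that the count for change from baseline "will include all participants who have both a baseline and a value at the nominal visit".

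For results that are not plain numbers, the same section sets three rules:

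- A strict inequality, in either direction, becomes a number by subtracting 0.001.
- A `≥` or `≤` result "will be converted to the end point".
- Then: "These numeric values will be evaluated for clinically significant abnormalities, but will not be included in calculations of summary statistics".

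Neither document reverses the exclusion or gives a substitute for it in the descriptive tables. SAP 5.2.10 shows the number of missing values for continuous variables, but does not say whether an excluded inequality counts as missing.

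The protocol's own laboratory outputs (Protocol 9.6.1, Laboratory Tests) are grades, normal/abnormal categories and shift tables: "Summary of laboratory abnormalities will be presented by maximum CTCAE Grade". The means and medians are added by the SAP.

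**The concern.** An inequality is an observed result lying beyond a laboratory's reporting limit. Dropping it is exclusion by outcome value, not random missingness, so what remains is a truncated distribution. A printed maximum can be lower than a result known to exceed it, and a printed minimum higher than a result known to be below it.

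The change rows have a further problem. A participant whose baseline is an inequality has a baseline, so the counting rule includes that participant at every visit with a value. Under the exclusion there is no number to subtract. The two sentences of SAP 6.6.1 cannot both be applied as written.

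At stake is how accurately the by-visit laboratory tables describe the data in a study whose primary objective is safety. A reader of those tables could not tell a test not done from a result beyond the limit. Tests are run at local laboratories (Protocol 7.2.4 and Appendix 3), so the excluded share may also differ by site.

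**Working it through.** **Plan's own figure.** The only design figure is the maximum standard error of an AE rate: √(0.5 × 0.5/100) = 0.05, which reproduces. It does not bear on this point.

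**Inputs.** The rule is from SAP 6.6.1, and n = 100 is from Protocol 9.2. The share p of results reported as inequalities is in neither document; I assume 1% to 20% per test. Values are taken as standard normal with one common lower limit at the p-th percentile z_p. Extremes come from 4,000 simulated data sets of 100.

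**Actual values, `<` results dropped (SD units).**

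- Mean shift = φ(z_p)/(1 − p). At p = 5%: 0.1031/0.95 = 0.109.
- Median shift = z at (1 + p)/2. At p = 5%: z(0.525) = 0.063.

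| p | Mean, dropped | Median, dropped | Minimum, dropped | Mean, set to limit | Minimum, set to limit |
|---|---|---|---|---|---|
| 1% | +0.03 | +0.01 | +0.43 | 0.00 | +0.28 |
| 5% | +0.11 | +0.06 | +0.94 | +0.02 | +0.86 |
| 10% | +0.19 | +0.12 | +1.27 | +0.05 | +1.22 |
| 20% | +0.35 | +0.25 | +1.70 | +0.11 | +1.67 |

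The maximum does not move in any row. With the limit substituted, the median shift is 0 throughout. Dropping `>` results mirrors this: at 5% the mean moves −0.11, the median −0.06, the maximum −0.94 and the minimum 0.

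**Both kinds present.** With 5% beyond each limit, the mean and median shift by about 0, the minimum by +0.96 and the maximum by −0.94.

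**Change from baseline.** Assume 10% below the limit, correlation 0.6 and no true change.

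- Only baseline results censored: (0.6 − 1) × 0.195 = −0.08 SD.
- Only visit results censored: (1 − 0.6) × 0.195 = +0.08 SD.
- Both censored: 0.00 by symmetry.

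**Different local limits.** If one of two equal-sized laboratories has a limit at the 20th percentile and the other has none, the minimum changes in only 50% of simulated data sets.

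**A skewed example (all inputs assumed).** Take log-normal bilirubin, median 0.5 mg/dL, CV 50%, limit 0.3.

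- σ = √ln(1.25) = 0.472, and the share below the limit is Φ(ln(0.6)/0.472) = 14.0%.
- The true mean is 0.559. After dropping it is 0.559 × Φ(0.472 + 1.081)/(1 − 0.140) = 0.611. With the limit substituted it is 0.567.
- The median is 0.543 after dropping, against 0.500.

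**Conversion rule.** `<10` gives 10 − 0.001 = 9.999. `>10` also gives 10 − 0.001 = 9.999, below the value it was reported to exceed.

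**The case against.** A reader might infer that the rule hides the largest toxic values. The documents do not support that. The quoted sentence keeps these results for evaluating abnormalities. Once converted they carry a numeric value, which is what SAP 6.6.1 requires for CTCAE grading. They then feed the shift table (SAP 3.5.1), worst grade by timepoint and overall, the liver-test categories, the eDISH plots and the liver listing. An ALT of `>1000`, converted to 999.999, meets the 10 × ULN category for any ULN up to 999.999/10, about 99.99 U/L. The by-visit tables are not the plan's tool for peaks in any case, because they leave out unscheduled results.

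A reader might also infer that mean, median, minimum and maximum are all wrong in a known direction. The working shows otherwise: one-sided dropping leaves the opposite extreme alone, limits on both sides roughly cancel in the mean and median, and the sign for change from baseline depends on which visit is censored.

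Three further objections have force:

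- Where local limits differ, rank is not always known. `<0.3` at one site cannot be ordered against 0.2 at another, and need not be extreme in the study.
- The frequency is assumed. It may be low for most tests in Protocol Appendix 3, Table 4, and at 1% the mean and median shifts are at most 0.03 SD.
- These tables go beyond what the protocol names, and SAP 5.1.1 has no hypothesis test.

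These limit the importance of the point. They do not supply a reason for dropping observed results without a count or a replacement rule.

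**Conclusion.** The point holds as a minor defect in the by-visit descriptive laboratory tables. For one common limit on one side, the bias in the mean, the median and the affected extreme has a known direction. At an assumed 5% of results it is about 0.11 SD for the mean (0.03 to 0.35 over 1% to 20%) and 0.06 SD for the median (0.01 to 0.25). The sizes rest on normal values and an assumed share of inequalities. No direction can be stated when both kinds of inequality occur or for change from baseline. The conflict with the counting rule for change rows stands whatever the frequency.

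The exclusion leaves grade, shift and liver-test summaries, AE incidence, ORR and DoR untouched. This reads summary statistics in the quoted sentence as the by-visit descriptive statistics. SAP 6.6.1 later uses the same term for counts by grade, so it should be defined.

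The conversion of `>` results is a separate slip in the same paragraph. It does reach the abnormality evaluation: a `>` result could be classified too low if its limit coincides with a grade or ULN-multiple cut-off.

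**What to change.** In SAP 6.6.1:

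1. Replace the last clause so that inequality results enter the by-visit and change-from-baseline summaries at the reporting limit. This also reconciles the rule with the counting sentence for change rows.
2. Footnote the number of such results per test and visit.
3. Print an affected minimum or maximum as `<limit` or `>limit`. Substitution alone does not repair the extremes: at 5% the minimum is still off by 0.86 SD.
4. Where such results are frequent, rely on the median and quartiles, provided they lie inside the measurable range of all contributing laboratories.
5. Correct the conversion to add 0.001 for `>` results. Do not use the present converted value for them in any table.
6. Say that summary statistics here means the by-visit descriptive statistics.

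The cost is a few sentences in one SAP section and a table footnote. Sample size, endpoints and data collection do not change. The downside is that the mean and SD then depend slightly on the substituted limit (mean bias of 0.02 SD at 5% and 0.11 SD at 20%, against 0.11 and 0.35 now), which the footnote discloses.

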9.1. Estimands and Statistical Hypotheses

This is a single arm study with no statistical hypothesis testing. The primary objective of the trial is to evaluate the safety and tolerability of single-agent dacomitinib for the first-line treatment of participants in India with metastatic NSCLC with EGFR activating mutations.

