13. DEFINITION OF END OF STUDY

13.1. End of Study

The end of study is defined as 1 year after the LPFV date in the study. At the end of study, participants who are on treatment and benefiting from dacomitinib treatment will be switched to commercially available dacomitinib if considered appropriate by the investigator, as soon as feasible.

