3.5.1. Laboratory Data

Hematology and chemistry result will be programmatically graded according to the NCI CTCAE version 4.03 for relevant parameters. A shift summary of baseline grade by maximum post-baseline grade will be presented. Parameters which cannot be graded will be summarized relative to the normal range (ie, normal range high or normal range low). Additional details are provided in [Section 6.6.1](#).

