5.2.2. Definition of Cycle and Cycle Day

Cycle start and end dates are derived per participant. Treatment will be dispensed at the beginning of every 28-day cycle.

- For Cycle X, the actual cycle start date for each participant is:
 - The earliest start date of dosing (dose>0 at that visit) in Cycle X visit case report form (CRF) exposure page.

- For all but the last cycle.
 - Actual cycle stop date is calculated as the start date of the next cycle minus one day.
 - Actual cycle duration is calculated from Day 1 of a cycle to the day prior to Day 1 of the next cycle, as follows:

$$\text{Actual Cycle Duration (weeks)} = (\text{cycle stop date} - \text{cycle start date} + 1)/7.$$

- For the last cycle, actual cycle duration is calculated as follows:
 - $\text{Actual Cycle Duration (weeks)} = (\text{last date of study treatment} - \text{cycle start date} + 1)/7.$

The cycle day will be calculated as:

$$\text{Cycle day} = \text{Date of the assessment/event} - \text{cycle start date} + 1.$$

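### The creatinine shift table grades baseline on ULN alone but later records on ULN or own baseline, which tilts it toward upward shifts; a ULN-only shift table should sit beside it (minor)

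*SAP*

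**What the plan says.** - **Grading.** SAP 6.6.1: "laboratory results will be programmatically classified according to NCI-CTCAE version 4.03 grade". Where criteria overlap, creatinine being the SAP's example, a value may meet one range against ULN and "another range based on comparison to baseline), the highest (worst) grade would be assigned to that record".
- **Baseline.** SAP 6.6.1: "baseline will be defined as the last assessment performed on or prior to date of the first dose of study treatment".
- **Display.** SAP 3.5.1: "A shift summary of baseline grade by maximum post-baseline grade will be presented". SAP 6.6.1 adds for the overall summary: "Worst case overall will be determined from scheduled and unscheduled visits".
- **Sampling.** The protocol's Schedule of Activities takes blood chemistry on Day 1 of every cycle and at end of treatment. SAP 5.2.2 sets the cycle length: "Treatment will be dispensed at the beginning of every 28-day cycle". Protocol 13.1: "The end of study is defined as 1 year after the LPFV date in the study".
- **Comparator.** Protocol 9.1: "This is a single arm study with no statistical hypothesis testing".

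Neither document prints the CTCAE creatinine cut-offs. No creatinine display in the SAP separates the two criteria.

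**The concern.** A shift table is read as a before-and-after comparison on one scale. Here the scale changes between the axes. The ratio of the baseline record to itself is 1, so a criterion that requires a rise over baseline can never grade it. After first dose that criterion is live at every record, and the worst result is kept. A participant whose creatinine stays within the normal range can thus move from Grade 0 to a positive laboratory grade through ordinary fluctuation, and no downward movement on that criterion can offset it.

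In a single-arm study no control column shows how much of the shift is background. A reader of the creatinine row could take some of it for a renal effect of the drug.

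**Working it through.** **The plan's own figure.** The only precision figure in the documents is the maximum standard error of an AE rate with 100 participants (Protocol 9.2): sqrt(0.5 x 0.5 / 100) = 0.05, as stated. It describes sampling error and says nothing about this asymmetry.

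**Number of post-baseline records.** One year is 365/28, or about 13 cycles. Cycle 1 Day 1 is baseline. Day 1 of Cycles 2 to 13 gives 12 records and end of treatment gives one more, so k = 13 for the last participant enrolled if treated throughout. Earlier enrollees treated throughout have more; participants who stop early have fewer.

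**Exact upper bound.** Suppose any rise above baseline earned a grade, values were continuous and there was no drug effect. Baseline and the k later values are then exchangeable, so P(at least one later value exceeds baseline) = k/(k+1):

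- k = 1: 1/2 = 50%
- k = 3: 3/4 = 75%
- k = 6: 6/7 = 86%
- k = 13: 13/14 = 93%

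**Simulation with no drug effect.** All of the following are assumptions, since the documents do not give them: lognormal creatinine, median 0.70 x ULN, between-subject log-SD 0.20, within-person CV 10%, ULN grades starting above ULN with a higher grade above 1.5 x ULN, and lowest versus-baseline grade starting above c x baseline. Each record takes the worse grade, and the maximum over k records is compared with the baseline grade. Percent of participants with an upward shift:

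| Rule | k = 1 | k = 3 | k = 6 | k = 13 |
|---|---|---|---|---|
| Worse of two, c = 1.0 | 48.8 | 72.4 | 82.2 | 88.6 |
| Worse of two, c = 1.1 | 25.1 | 46.1 | 59.5 | 71.8 |
| Worse of two, c = 1.25 | 7.5 | 17.1 | 25.7 | 36.9 |
| Worse of two, c = 1.5 | 2.9 | 6.5 | 9.9 | 14.5 |
| ULN only, both axes | 2.7 | 6.0 | 9.1 | 13.1 |

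**What the combined rule adds at k = 13:** 88.6 - 13.1 = 75.5 points (c = 1.0); 71.8 - 13.1 = 58.7 (c = 1.1); 36.9 - 13.1 = 23.8 (c = 1.25); 14.5 - 13.1 = 1.4 (c = 1.5).

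**Separating the two causes.** At one visit no maximum is involved. ULN-only rises and falls then balance (2.7% against 2.8%), while the combined rule with c = 1.0 gives 48.8% rises against 2.8% falls. That imbalance comes from the grading rule alone. The growth of the ULN-only row from 2.7% to 13.1% comes from the maximum alone.

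**Sensitivity at k = 13.**

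- Median 0.85 x ULN, CV 10%: 75.4, 64.8, 43.5 and 30.8% for c = 1.0, 1.1, 1.25 and 1.5, against 30.1% on ULN alone.
- Median 0.85 x ULN, CV 5%: 74.5, 40.1, 14.5 and 14.0%, against 14.0%.
- Median 0.70 x ULN, CV 5%, c = 1.5: 4.8% under either rule.
- Median 0.70 x ULN, CV 10%, c = 1.0, values rounded to 0.1 mg/dL with ULN taken as 1.2 mg/dL: 80.4% in place of 88.6%.

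**The case against.** The strongest reply is that this is simply CTCAE v4.03. Protocol 9.6.1 requires that scale for laboratory results, a baseline criterion exists to detect rises within the normal range, and taking the worse grade is conservative in a safety study. This stands as a reason not to replace the combined grade. It does not stand against adding a display, because the two-axis table is the SAP's own choice. SAP 6.6.1 already summarises each direction separately for tests graded both high and low.

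Second, other planned output limits the harm. SAP 6.6.1 also summarises actual values and change from baseline by nominal visit, where a mean change near zero would warn the reader. Its worst grade by scheduled timepoint does not accumulate over visits. This stands in part: the by-timepoint grades keep the asymmetry, and the visit-level summaries exclude unscheduled tests and cannot show which graded participants ever exceeded ULN.

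Third, the size is not fixed by the documents. This stands in full: at a 1.5 x cut-off the combined rule adds almost nothing.

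Three stronger readings are tempting, and the documents do not support them:

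- *The primary endpoint is inflated.* Under Protocol 8.5 an abnormal result becomes an AE only through symptoms, further work-up or intervention, a change in dosing or other therapy, or the judgement of the investigator or sponsor. AEs are graded by the investigator. Programmed laboratory grades are a separate display.
- *ULN-only grading would show almost no shifts.* That holds only if every value is assumed normal. Protocol 4.1 admits creatinine clearance down to 30 mL/min, so some baselines may lie near or above ULN.
- *The growth with visits is all due to the baseline criterion.* Any maximum over visits grows, for every graded analyte.

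**Conclusion.** The asymmetry is real and follows from the SAP's rules alone: the creatinine shift table is biased toward upward shifts without any drug effect. How much is undetermined. Under the main assumptions (median 0.70 x ULN, CV 10%, 13 records) the excess over ULN-only grading runs from about 1 point if the lowest versus-baseline grade starts above 1.5 x to about 75 points if it starts just above 1.0 x. The sponsor holds the cut-off and can settle this at once. Repeated sampling would still raise the ULN-only figure, from about 3% at one visit to about 13% at 13, so the number of assessments has to be shown as well.

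The effect is confined to creatinine within the laboratory grade displays. AE incidence, the sample-size statement and the response endpoints are not directly affected, and no hypothesis test depends on it. Severity: minor.

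**What to change.** In SAP 3.5.1 and 6.6.1, keep the combined CTCAE v4.03 grade as planned and add for creatinine:

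1. a shift table in which baseline and post-baseline records are both graded on the ULN criterion only;
2. a separate row counting participants whose post-baseline grade arises solely from the versus-baseline criterion, so that rises within the normal range stay visible;
3. the number of post-baseline creatinine assessments per participant, summarised beside the table, since the first two items do not remove the growth that comes from taking a maximum.

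A footnote to the combined table should say that the versus-baseline criterion cannot apply to the baseline record, and should state the lowest multiple used.

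Cost: one extra laboratory display and a few lines of SAP text. No new data are needed, and the protocol's CTCAE requirement is still met.
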